### ***Randomization and blinding***

The biostatistician block-randomizes assignment of the ITT population to treatment (sham vs. active) using a 1:1 allocation ratio and, within each treatment group, stratification by sex (male/female) and non-opioid substance use disorder (presence/absence). The master codebook for randomization is kept in a secure location at Wayne State University and only the biostatistician and a research assistant (backup person) can access it.

Sham treatment, which controls for placebo effects, is designed to minimize sham recognition by the sponsor, principal investigator, participants, research assistants and treatment staff (i.e. quintuple blinding). Participants in the active arm receive standard NET treatment. Participants in the sham arm receive the same standard NET treatment as the active arm but will receive no electrical stimulation (cable is disabled beforehand). Sham credibility is evaluated for both arms based on surveys following the 1-hr treatment phase, and daily during device use. A single ‘treatment perception’ question asks: “How confident are you that you are receiving the real device treatment and not the placebo (sham) treatment?” Three ‘device satisfaction’ questions ask: (1) “How satisfied are you with the NET Device?” (2) “How willing are you to use the NET Model 901 Device?” and (3) “How willing are you to recommend the NET Model 901 Device to other people undergoing opioid discontinuation?”

Active and sham arms will receive identical device care and use instructions, identical equipment, attachment methods and locations, and identical daily reviews of device operation, electrode attachment, and withdrawal severity. The treatment apparatus presents both active- and sham-assigned participants with visual cues from the device’s “heartbeat” indicator (a blinking green light-emitting diode which indicates the device is active) during treatment. Research staff instruct each participant that the equipment is designed to be self-administered, that s/he can set the level of stimulation wherever it is comfortable, that stimulation is not always (and does not need to be) sensate, and that device use may be discontinued when s/he feels it is providing no benefit.

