### ***Participant selection criteria***

Screening includes informed consent, HIPAA authorization, assessment of demographics, contact data, pregnancy testing, contraception methods, medical history, and urine drug testing (including fentanyl, buprenorphine, and methadone). Assessments are aligned with the treatment

facility's standard of care such that electronic case report forms (eCRFs) can be rapidly reviewed for study eligibility by the remote investigator, given the time-sensitive nature of enrollment.

During the recruitment and informed consent process, participants are repeatedly told they can receive FDA-approved MOUD at the treatment facility instead of participating in the study. They are also told that upon discontinuation of device stimulation, and/or if they drop out of the study, they can receive TAU (including MOUD) at any time. All participants are given a "loss-of-opioid tolerance" warning (i.e. stopping opioids leads to reduced tolerance, and subsequent opioid use increases their risk of overdose and death), which they must sign. Participants are also given a naloxone kit upon discharge from the treatment facility and educated on its use. All of these procedures are documented in the medical record and case report forms.

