Participant withdrawal. Participants can withdraw from the study at any time on request. Discontinuation of device use prior to completing the minimum 1-hr treatment period constitutes withdrawal from the study. The investigator may discontinue or withdraw a participant from the study for the following reasons: (1) significant study intervention non-compliance; (2) if any clinical adverse event (AE), laboratory abnormality, or other medical condition or situation occurs such that continued participation in the study is not in the best interest of the participant; (3) disease progression which requires discontinuation of the study intervention; (4) if the participant meets an exclusion criterion (either newly developed or not previously recognized) that precludes further study participation; or (5) participant is unable to receive treatment following enrollment.

Participants who sign the informed consent form and are randomized but do not receive the study intervention will be replaced. Participants who sign the informed consent form, are randomized, receive the study intervention, and subsequently withdraw or are withdrawn, will be replaced.

Participants who withdraw from the study will receive TAU as defined by treatment staff (who are independent of the research staff), where such care may include MOUD.

Lost to follow-up. A participant is considered lost to follow-up if s/he becomes unavailable for all video assessments following discharge from the inpatient environment.

Populations for analysis. The ITT analysis dataset and the safety analysis dataset will contain all randomized participants. The per-protocol analysis dataset will contain the subset of the ITT dataset who: (1) present with a COWS score of moderate or above; (2) receive at least 1 hr treatment from the device; and (3) complete at least one post-discharge video interview.

Efficacy endpoints. The primary analysis will assume that data came from a mixed-effect linear model. Each model will include a random intercept, fixed effect for treatment, participant-specific random effect and covariate corresponding to duration of inpatient residence. The primary hypothesis involves testing the main effect for treatment difference between the groups (sham vs. active). A likelihood ratio test will examine the group effect focusing on the primary hypothesis.

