Secondary endpoint analyses are not powered, but may be used to demonstrate additional benefits of the treatment, provided it has been demonstrated that the primary endpoint shows clear statistical significance, as well as clinical meaningful benefits of the treatment [19]. Analysis of the secondary endpoint resembles primary endpoint analysis, using mixed-effect model testing for the between-group main effect.

Given that participants can control the level of device stimulation, exploratory regression analyses will seek to identify potential relationships between device utilization (e.g. number of minutes device ‘on’ [non-zero intensity], average intensity while device ‘on’) and efficacy endpoints.

Expected outcomes. We selected a single primary outcome (abstinence without MOUD). From our past experience at this same treatment facility, the expected group means for sham and NET arms are 0.48 and 3.97 weeks of average opioid abstinence with standard deviations 1.19 and 3.46, respectively. This results in effect size of 1.12. This effect size based on pilot data is rather large,

which is often the case due to limited scope of the pilot study. Thus, we took a conservative approach as suggested by Kraemer et al. [20] with moderate effect size of 0.45.

Safety endpoints. Secondary safety endpoints (AEs, SAEs, ADEs, SADEs, UADEs and device deficiencies) will be summarized using descriptive statistics.

Subgroup analysis. The analysis will stratify by sex (male/female) and non-opioid SUD (presence/absence). The expected outcome is that allocation on those variables will be balanced between the two groups. It is not anticipated that the primary outcome (opioid abstinence without MOUD) will differ across these subgroups. If significant baseline group imbalance is detected on any variable and its correlation with outcome ( $\geq 0.30$ ), that variable will be included as a covariate in the inferential analyses. If systematic variation is noted by any subgroups for primary or secondary outcomes, further exploration will be conducted via cluster analysis.

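### The only stated route for a baseline covariate into the primary model is an imbalance-and-correlation rule that needs outcome data, so the model is not fixed in advance and prognostic baseline data are nearly always left out

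*Combined protocol and SAP*

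**What the plan says.** The Efficacy endpoints paragraph of the Statistical analysis plan defines the primary model: "Each model will include a random intercept, fixed effect for treatment, participant-specific random effect and covariate corresponding to duration of inpatient residence". It then says: "A likelihood ratio test will examine the group effect focusing on the primary hypothesis". Length of inpatient stay is known only after randomization, so the model as listed contains no pre-treatment variable.

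The Subgroup analysis paragraph adds a conditional rule: "If significant baseline group imbalance is detected on any variable and its correlation with outcome" (at least 0.30), "that variable will be included as a covariate in the inferential analyses". The primary test is not exempted, and the plan states no other way for a baseline variable to enter. It does not list candidate variables, name the imbalance test or its significance level, or say what kind of correlation is meant or whether it is judged blind to arm.

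Pre-treatment data are nevertheless collected. The Participant selection criteria section describes "urine drug testing (including fentanyl, buprenorphine, and methadone") at screening. The schedule of activities (Figure 3) also shows drug use history at screening, and COWS, craving, DASS-21, PANAS and Epworth at the Day 1 baseline.

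**The concern.** There are two problems.

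First, the model for the single confirmatory test is not fixed. Whether a variable meets the condition on "its correlation with outcome" cannot be known until outcomes exist. With no candidate list, test or level, two statisticians could follow the rule faithfully and fit different primary models.

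Second, the rule selects on the wrong property. In a randomized trial, any baseline difference between the arms is due to chance, so testing it for significance says nothing about whether adjustment is worthwhile. Precision comes from prognosis. A strongly prognostic variable that happens to be balanced is never used, although adjusting for it would still reduce the residual variance.

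At stake are some power for the primary comparison and a primary model that could be argued over afterwards.

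**Working it through.** **Inputs from the plan.** 50 per arm, 1:1 (Study design); standardized effect 0.45 (Sample size determination); correlation cut-off 0.30 (Subgroup analysis).

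**Assumed, because not stated.** Two-sided 5% for the primary test; 5% for the imbalance test; the cut-off applied to the absolute correlation; all baseline-outcome correlations.

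**1. The plan's own figure.** The plan claims sufficient power at N=100 for an effect of 0.45, but gives no power level, alpha or sidedness, so there is no exact figure to match. By the normal approximation, 0.45 × √(50/2) = 2.25.
- Two-sided 5%: Φ(2.25 − 1.96) = Φ(0.29) = 61.4%.
- One-sided 5%: Φ(2.25 − 1.645) = Φ(0.605) = 72.7%.
- At the N=125 also mentioned in the Missing data paragraph: 71.1% and 80.8%.

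**2. How often the rule admits a covariate.** Entry needs p<0.05 for imbalance and an observed correlation of at least 0.30. At n=100, the chance that the observed correlation reaches 0.30 is 0.50 if the true value is 0.3, and 0.991 if it is 0.5.
- True r = 0.3: 0.05 × 0.50 = 2.5%. Simulated: 2.3% to 2.6%.
- True r = 0.5: 0.05 × 0.991 = 5.0%. Simulated: 4.9% to 5.2%.

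A prognostic covariate is therefore left out in about 95% or more of trials. The chance of at least one significant imbalance among independent candidates is 1 − 0.95^8 = 34% for 8, 1 − 0.95^10 = 40% for 10, and 1 − 0.95^15 = 54% for 15.

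**3. Power under three strategies** (simulation, linear model, independent normal covariates, without length of inpatient stay):

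| Prognostic covariates | Unadjusted | Plan's rule | Fixed in advance |
|---|---|---|---|
| One, r = 0.3 | 60.0% | 59.9% | 63.9% |
| One, r = 0.5 | 60.1% | 60.8% | 72.1% |
| 15 candidates, four prognostic (r = 0.35, 0.30, 0.25, 0.20) | 61% to 62% | 61% | 75% to 76% |

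In the last row, joint R² = 0.1225 + 0.09 + 0.0625 + 0.04 = 0.315, and the rule triggers in 8% to 9% of trials.

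**4. Type I error.** Under the rule, simulated type I error was 3.4% to 4.5% across scenarios. With covariates fixed in advance it was 4.5% to 4.8%.

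**5. How the gain depends on prognostic strength.** The simple formula replaces d by d/√(1 − R²) and ignores the cost of estimating the covariates. Simulation with five covariates includes that cost; the ranges span separate runs. Unadjusted power was about 0.60 to 0.62.

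| Joint R² | Five covariates, simulated | Simple formula |
|---|---|---|
| 0 | 0.57 to 0.59 | 0.61 |
| 0.05 | 0.59 to 0.61 | 0.63 |
| 0.10 | 0.62 to 0.63 | 0.65 |
| 0.20 | 0.67 to 0.68 | 0.70 |
| 0.30 | 0.74 to 0.75 | 0.76 |

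Break-even for five covariates is therefore at a joint R² between about 0.05 and 0.10.

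**The case against.** The strongest reply is that the rule itself does little harm. Power under it matches the unadjusted analysis, and type I error does not exceed 5%. A reader might infer that choosing covariates after seeing outcomes inflates false positives; the simulations do not show that for mechanical application. The exposure lies in the discretion that the wording leaves. In an illustrative check, taking the smallest p-value among the unadjusted model, the rule model and models adding one variable imbalanced at p<0.10 gave 6.1%. That would be misuse, which the plan does not propose.

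The gain comes from adding prognostic covariates, and the documents give no baseline-outcome correlation. A joint R² of 0.315 assumes four uncorrelated predictors. The plan expects a sham mean of 0.48 weeks (SD 1.19), an outcome crowded near zero that a normal model represents poorly. The plan's 0.45 is defined after adjustment for inpatient stay, which the simulations omit. A one-sided test or N=125 would raise the starting power. All of this stands, so the gain is a range, and it can be a small loss.

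A conditional bias can also be constructed. An imbalance at exactly p=0.05 is 1.984 × √(2/50) = 0.397 SD; with r = 0.29 it would go unadjusted and leave 0.397 × 0.29 = 0.115 SD, or 26% of 0.45. This is a knife-edge case that averages to zero over randomizations, and deleting the rule would not remove it for a variable outside the fixed list.

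Two further readings go beyond the text: that strong negative correlations are deliberately ignored (the sentence is grammatically incomplete, and absolute value is the natural sense), and that the rule would be run unblinded (arm labels could be masked; the plan does not say). Finally, the rule says if, not only if, but no other route is given. The sentence about stratifying by sex and non-opioid SUD could bring in those two factors, but it sits under Subgroup analysis and does not affect other baseline variables.

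**Conclusion.** The point holds as a cheap improvement; the trial is not invalid without it. As written, the primary model's covariate set is settled only after outcomes are available, by a rule that cannot be reproduced from the text, and a prognostic baseline variable is left out in about 95% or more of trials. The rule recovers essentially none of the precision on offer.

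The documents do not support reading this as type I error inflation, as a demonstrated bias, or as precision available at no cost. On the assumptions above, five fixed covariates range from roughly no gain, or a slight loss, at a joint R² of 0.05 to about 0.13 to 0.14 more power at 0.30 (0.74 to 0.75, less the simple-formula unadjusted value of 0.61). The specific power figures should not be relied on, because every correlation is assumed.

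**What to change.** Before any unblinded outcome data are examined, amend the SAP to:

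- Name a short fixed set of about two to four pre-treatment variables expected to be prognostic, and include them in the primary and secondary models whatever the observed balance. Examples are Day 1 craving, baseline DASS-21 total and screening-urine opioid status. Day 1 COWS is a weaker candidate, because the entry threshold restricts its range.
- Remove the imbalance-and-correlation rule from the primary analysis. If it is kept, label it a sensitivity analysis and give it a candidate list, test, level and absolute-value cut-off.
- Report baseline balance descriptively, without p-values.
- State a simple rule for missing baseline values.

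The timing matters: the Outcome measures section speaks of the study as already begun, and the biostatistician has access to the randomization codebook. The date of the list, and the fact that it was fixed without sight of outcomes by arm, should be documented.

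The cost is a few degrees of freedom, with a small loss of power if the covariates prove not to be prognostic. It is not purely a wording change. Figure 3 marks the screening drug screen as paper source, and the Data & safety monitoring section says that only specific eCRF data are exported for analysis, so availability of the chosen screening values in the analysis database must be confirmed. The baseline DASS-21 also needs confirming: Figure 3 schedules it on Day 1, but the Outcome measures text mentions depression, anxiety and stress only at the end of the inpatient and outpatient phases.

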### ***Study design***

This ITT, randomized, single-site trial uses a superiority design that compares active treatment to sham control. This trial will evaluate efficacy and safety endpoints during opioid discontinuation within an inpatient setting, and subsequent outpatient assessment of opioid and non-opioid substance use following discharge (primary and secondary endpoints, respectively). Fifty participants will be randomized to each of the two treatment arms (active and sham) and prospectively followed. **Figure 2** illustrates the study schema. **Figure 3** illustrates the schedule of activities.

As the platform for this trial, all participants receive treatment as usual (TAU), except MOUD, which they choose (as part of informed consent) not to receive as a condition of inclusion in this study. Participants could experience clinical deterioration during inpatient discontinuation of illicit opioids, prescribed opioid agonist medications (buprenorphine, methadone), and other illicit substances. Participants are instructed that device use (active or sham treatment) is self-administered, they may discontinue device use at any time and for any reason and can receive TAU for their clinical condition including MOUD and comfort medications.

The rationale for the minimum 1-hour device treatment period is to ensure a controlled degree of exposure to the device (active or sham) for all participants; based on prior open-label studies, the active device produces benefits in about 15-20 min. Completing this 1-hr period triggers study follow-up assessments. The rationale for the 7-day maximum device treatment period is to limit variability in the duration of exposure (to be treated as a covariate in analyses); as **Figure 1** indicates, the majority of participants stop active device use after about 7 days.

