## ***Statistical analysis plan***

Sample size determination. Sample size is based on statistical power analyses for the primary hypothesis based on single primary outcome (opioid abstinence without MOUD). A conservative approach was used to preserve power with a smaller effect size than observed from prior uncontrolled, non-blinded intervention studies with the NET Device. Power analyses examined sample sizes required to detect clinically meaningful group differences between sham and active groups. This represents standardized difference between the two groups after adjusting for the effect of the covariate “duration of inpatient residence” (which is capped at 28 days). Sample size determination was carried out *via* simulation in R-software; 5000 iterations were run in which group means were generated using a mixed-effect additive model. Sample size is a function of hypothesized effect size (standardized group difference) and the sign and magnitude of the regression coefficient (duration of inpatient residence). With projected N=100 (enrolled) there will be sufficient power to detect a standardized effect size of 0.45 or higher.

Missing data. In this ITT design, a participant is “included” (becomes part of the evaluable ITT data set) when he/she completes 1-hr of device use. We expect only 5% attrition, i.e. for 100 participants who complete 1-hr of device use, we expect to consent 105 individuals. A comparable trial of a

percutaneous electrical stimulation device for treating opioid withdrawal symptoms found that 71 of 73 enrolled participants completed 1-hr of device use, only 2.8% attrition [18]. **Table 1** explains how missing data are handled, i.e. for the primary efficacy endpoint, missing data are imputed as “not opioid abstinent without MOUD”. The definition of the primary endpoint (“opioid abstinence without MOUD”) and secondary endpoint (“non-opioid abstinence”) thus covers any intermittent missing values and loss to follow-up, and is not expected to impact power of the primary analysis. Premature study termination (e.g., death, relocation, or adverse events) may result in missing data, although this attrition is expected to be low. The projected sample size (N=125) was increased to cover unforeseen events.

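### The subgroup plan follows up an undefined trigger with cluster analysis and specifies no treatment-by-subgroup interaction, so chance differences between strata could be read as effect modification

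*Combined protocol and SAP*

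**What the plan says.** The subgroup paragraph of the statistical analysis plan names two factors with two levels each, sex and non-opioid SUD. Both are also randomization strata (Randomization and blinding). The paragraph says in advance: "It is not anticipated that the primary outcome (opioid abstinence without MOUD) will differ across these subgroups". It gives a rule for adding imbalanced baseline variables as covariates, and ends with the follow-up step: "If systematic variation is noted by any subgroups for primary or secondary outcomes, further exploration will be conducted via cluster analysis".

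The models contain no term for effect modification. For the primary endpoint, under Efficacy endpoints: "Each model will include a random intercept, fixed effect for treatment, participant-specific random effect and covariate corresponding to duration of inpatient residence". For the secondary endpoint: "Analysis of the secondary endpoint resembles primary endpoint analysis, using mixed-effect model testing for the between-group main effect".

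The plan gives no test, threshold or multiplicity rule for deciding that outcomes vary systematically. Nor does it limit the subgroups in the last sentence to the two named factors.

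**The concern.** The useful subgroup question in a sham-controlled trial is whether the active-minus-sham difference varies by sex or by SUD status. A treatment-by-factor contrast estimates that directly. Cluster analysis answers a different question, namely which participants resemble one another, and gives no estimate, interval or test of a difference in treatment effects.

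With no interaction term and no definition of the trigger, the analyst has only stratum-specific results to go on. At 50 per arm each stratum is small, so one stratum can easily look positive and the other not when the true effect is the same in both. An unsupported impression that the device works in one sex, or only in people without another SUD, could then enter the report. The protocol describes the study as FDA-qualifying, so such a statement could matter beyond the publication.

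**Working it through.** **Inputs from the documents.** Arm size: "Fifty participants will be randomized to each of the two treatment arms (active and sham) and prospectively followed". Design effect: "With projected N=100 (enrolled) there will be sufficient power to detect a standardized effect size of 0.45 or higher". The pilot effect size is 1.12 (Expected outcomes). There are two binary factors and two efficacy endpoints, one primary and one secondary.

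**Assumptions, because the documents are silent.** Two-sided alpha of 0.05; normal outcomes with equal variance; the same true effect d (in SD units) in every participant; subgroup splits of 25/25, 30/20 or 35/15 per arm; and a reading rule under which a split means p<0.05 in one half and not in the other. The plan states no subgroup operating characteristics, so it has no figure to reproduce here.

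**Step 1. Power within a stratum.** For n per arm, use the noncentral t with 2n−2 degrees of freedom and noncentrality d·√(n/2). At d=0.45:
- n=25: noncentrality 0.45×√12.5 = 1.59, power 0.345
- n=30: power 0.403; n=20: power 0.284
- n=35: power 0.459; n=15: power 0.222

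**Step 2. Chance that exactly one half is significant.** This is p₁(1−p₂) + p₂(1−p₁).
- 25/25: 2×0.345×0.655 = 0.452
- 30/20: 0.403×0.716 + 0.284×0.597 = 0.458
- 35/15: 0.459×0.778 + 0.222×0.541 = 0.477

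**Step 3. The same calculation at other true effects, per factor.**

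| True effect d | Exactly one half significant (25/25 to 35/15) |
|---|---|
| 0 | about 10% (2×0.05×0.95 = 9.5%) |
| 0.2 | 19% |
| 0.45 (design value) | 45–48% |
| 0.8 | 33–45% |
| 1.12 (pilot value) | 5–16% |

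A simulation of 20,000 trials with two crossed factors agrees at d=0.45: 45–48% per factor, and 61–63% for at least one of the two factors.

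**Step 4. What an interaction test would do.** In the same simulation it rejects in about 5% of trials per test at every d tried (0, 0.45 and 1.12). Over two independent tests the chance of at least one false positive is 1−0.95² = 9.75%. Over four (two factors, two endpoints) it is 1−0.95⁴ = 18.5%, and 17–19% in simulation.

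**Step 5. What an interaction test cannot do.** For strata of n₁ and n₂ per arm, the standard error of the interaction is √(2/n₁ + 2/n₂) SD. The interaction detectable with 80% power is (1.96+0.84) times that.

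| Split per arm | SE | Detectable at 80% power | Power for a 0.45 SD interaction |
|---|---|---|---|
| 25/25 | 0.400 | 1.12 SD | 20% |
| 30/20 | 0.408 | 1.14 SD | 20% |
| 35/15 | 0.436 | 1.22 SD | 18% |

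**The case against.** A reader might infer that chance differences *will* be reported as effect modification. The documents do not support that. The plan calls the follow-up exploration, expects no subgroup difference in the primary outcome, and nowhere says that subgroup findings will be claimed or used for labelling. The trigger could also refer to outcome levels that differ between subgroups (prognosis) and not to treatment effects that differ. The nearby sentences on balance and covariate adjustment make that reading plausible. This objection stands, and the point is therefore about what could be misread.

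A reader might also take 45% as the plan's error rate. It is not. The significant-in-one-half rule is an inference, since the plan states no rule, and 0.45 gives the highest rates among the effect sizes tried. It is a fair value to show because it is the design value, but only alongside the range.

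Finally, a reader might infer that clustering undermines the randomized comparison. The clustering inputs are not given, and a later exploratory clustering leaves the primary test as it was. Comparisons of arms within clusters would lose the protection of randomization only if outcomes entered the clustering.

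None of this rescues cluster analysis as a way to examine effect modification. If the trigger means prognosis only, the plan has no method for effect modification at all. The ambiguity is part of the problem.

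**Conclusion.** The point holds as a weakness in an exploratory analysis. The planned follow-up cannot answer whether the treatment effect differs by sex or SUD, the trigger is undefined, and no interaction is specified. Chance differences between strata could therefore be misread. The primary hypothesis test and the sample size are not affected.

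The size depends on assumptions the documents do not supply. At the design effect, comparing significance between strata would show a spurious split in a little under half of trials per factor; with no effect, or with the pilot effect and equal halves, it would do so in a tenth or fewer. An interaction test holds the false-positive rate near 5% per test whatever the common effect. At this sample size it limits false claims but cannot rule out real effect modification. It should be changed because a better-suited method is available at little cost.

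**What to change.** Replace the cluster-analysis sentence with:

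> Effect modification by sex and by non-opioid SUD will be assessed by adding the factor main effect and the treatment-by-factor term, one factor at a time, to the primary and secondary models. Interaction estimates with 95% CIs and subgroup-specific differences will be reported as exploratory, without multiplicity adjustment; power is low (about 18–20% for a 0.45 SD interaction), so a non-significant interaction will not be taken as evidence of a homogeneous effect.

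The factor main effects are needed because the current models contain neither sex nor SUD status.

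The cost is SAP wording and two added terms per factor (main effect and interaction) for each endpoint. Both factors are used for stratified randomization, so no new data are required. The interaction estimates will be imprecise, and four unadjusted tests carry about an 18.5% chance of at least one false positive, which is why the exploratory label should stay.
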